## 4.2 END OF STUDY DEFINITION

A participant is considered to have completed the study after she has completed all phases of the study including the last visit at 8 weeks postpartum.

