## 3 OBJECTIVES AND ENDPOINTS

Aim	Variable	Description	Source
Maternal Outcomes			
1a	Breastfeeding	Exclusive breastfeeding : own mother's milk via breast or bottle. Predominant breastfeeding : greater than 75% of the infant's diet is their own mother's milk; the remainder of the diet is formula, donated milk, or other supplemental foods Mixed Breastfeeding : 25-75% or more of the infant's diet is their own mother's milk Predominantly supplementing : <25% diet is breastmilk No breastfeeding : infant is not consuming own mother's milk	End of weeks 2-8
1a	Supplementation type	Donated breastmilk, formula, other milks (cow, plant-based, nut), juice, water, cereal, other foods	End of weeks 2-8
1b	Progestin-only pill use	Any use, timing of initiation of POP use (assigned), type of POP (assigned), number of missed pills	End of weeks 2-8.
1b.	Contraception use	Sterilization (male and female), intrauterine devices, subdermal implants, oral contraceptives (combined), condoms (male and female), injectables, emergency contraceptive pills, patches, diaphragms, sponges, cervical caps, spermicidal agents, vaginal rings, withdrawal, fertility awareness, abstinence, and LAM	4 and 8 weeks
	Vaginal bleeding	Number of days of any bleeding and spotting in last month	Estimated at 4 and 8 weeks
	Satisfaction with contraception	Satisfied with method, would recommend method to a friend	4 and 8 weeks
	Pregnancy	Self-reported new pregnancy, pregnancy intendedness, whether planning to continue the pregnancy or not, and pregnancy outcome: continued, terminated, pregnancy loss	4 and 8 weeks
Milk Outcomes			
2	Composition of breastmilk	Fat, protein, carbohydrate (including oligosaccharide) content of milk	4-week breastmilk sample
	Maternal perception of adequate milk supply	Hill and Humenick Lactation Scale	End of weeks 2-8
Infant Outcomes			
3	Change in infant growth	Weight, length, and head circumference	Change between baseline and 4 weeks

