## 4 STUDY DESIGN

### 4.1 OVERALL DESIGN

This is a three-arm, placebo-controlled, double-blinded randomized controlled pilot trial that includes 8 weeks of participation from enrollment to final follow-up.

We hypothesize that the type of progestin used and the timing of progestin initiation will not have clinically meaningful effects on breastfeeding continuation, supplementation, the composition of breastmilk, or infant growth and body composition. In addition, we hypothesize that the timing of progestin initiation will not have a meaningful effect on progestin-only pill (POP) continuation, but that women will be more likely to continue d-POPs compared to n-POPs. Findings from this study will support more women to use progestin-containing contraceptives to prevent unintended pregnancy in the postpartum period with a greater understanding of the safety while breastfeeding.

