#### **Randomization:**

A licensed medical provider on the clinical care team will review eligibility for the method and instruct patients on use of POPs prior to discharge from the hospital and will approve a prescription for both POPs. Participants will then be randomized to (1) early d-POPs to be initiated at 120-168 hours (5-7 days) after delivery, (2) early n-POPs to be initiated at 120-168 hours after delivery, or (3) placebo for 28 days followed by d-POPs initiated at 4 weeks (28-35 days) after delivery, at a 1:1:1 ratio (Figure 2). Study staff will then provide participants with written and verbal instructions about when to initiate the method and to take the study medications in the order dispensed. Participants, care providers, and research staff will be blinded to group assignment. Participants will be instructed on lactational

amenorrhea method (LAM), a highly effective form of contraception, and will be counseled that if they no longer meet criteria for LAM, then they may be at risk for unintended pregnancy between days 28 and 33 and should use condoms or abstain from intercourse during that time. Before day 28, the CDC Selected Practice Recommendations state that a provider can be “reasonably certain that woman is not pregnant” regardless of LAM use and after day 33 all study drugs will be effective contraception regardless of group assignment.

The research team will dispense two 28-day pill packs containing either d-POPs, n-POPs, or one placebo and one d-POPs, as determined by the randomization scheme, and labeled 1st and 2nd. For participants in group 3, the first pack will contain only placebo to facilitate delayed initiation while ensuring blinding. D-POP packs will include 24 active and 4 placebo tablets per month, and n-POP packs will include 28 active tablets, packaged in order of daily use. All d-POP, n-POP, and placebo tablets will be encapsulated by the research pharmacies to have an identical appearance.

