**Figure 2: Outcome Evaluation Study Design**

**Surveys:**

Investigators will send participants hyperlinks via 5 text messages weekly at the end of weeks 2, 3, 5, 6, and 7 PP. Hyperlinks will lead to a brief questionnaire that participants can complete through a smartphone or tablet. Participants will complete a tablet-based survey in person at their 4 week visit. Participants will receive an emailed hyperlink at the end of week 8 which will lead to a longer questionnaire. A telephone survey will be available as an alternative to the digital questionnaires if desired. Survey questions will address continuation of and satisfaction with breastfeeding, the use of supplemental feeding, types of supplemental feeding being used, use of contraception, and satisfaction with contraception.

At 8 weeks PP, participants will be emailed and requested to complete a more detailed questionnaire eliciting breastfeeding continuation, supplementation amount and type, episodes of lactation support, perception of adequate milk supply, vaginal bleeding patterns, satisfaction with breastfeeding and

contraceptive use, satisfaction with contraception, infant health and well-being, and any new pregnancies and respective pregnancy outcomes if available. Additional potential confounding factors will be explored, such as use of nipple shields, pacifiers, breastmilk expression, and other medications the participant is using. Participants will receive a gift card via text or email link for each completed survey.

Both text and email questionnaires will be sent via a hyperlink that connects to a HIPAA-compliant secure platform that will input the data directly into a REDCap database. Participants who do not have smartphones or email access will be offered participation instead using phone surveys administered by study staff and gift cards will be mailed to these participants.

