##### **8.3.2 DEFINITION OF SERIOUS ADVERSE EVENTS (SAE)**

An adverse event (AE) or suspected adverse reaction is considered "serious" if, in the view of either the investigator or sponsor, it results in any of the following outcomes: death, a life-threatening adverse event, inpatient hospitalization, a persistent or significant incapacity or substantial disruption of the ability to conduct normal life functions, or a congenital anomaly/birth defect. Important medical events that may not result in death, be life-threatening, or require hospitalization may be considered serious when, based upon appropriate medical judgment, they may jeopardize the participant and may require medical or surgical intervention to prevent one of the outcomes listed in this definition.

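### The dispensed capsules run to day 60-62 but the last scheduled contact is on day 56, so no safety or pregnancy query follows the last dose

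*Combined protocol and SAP*

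**What the plan says.** **End of observation.** Section 4.2 counts a participant as complete "after she has completed all phases of the study including the last visit at 8 weeks postpartum". Under Surveys in section 8.1 that last contact is a link rather than a visit: "Participants will receive an emailed hyperlink at the end of week 8". Nothing is scheduled after it. Section 4.1 uses a different anchor: "8 weeks of participation from enrollment to final follow-up".

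**Supply.** Under Randomization in section 8.1: "The research team will dispense two 28-day pill packs containing either d-POPs, n-POPs, or one placebo and one d-POPs". The early arms start on day 5-7 ("early d-POPs to be initiated at 120-168 hours (5-7 days) after delivery"), and Group 3 starts its placebo pack in the same period. Section 6.1 gives the start window as 120-160 hours instead. A d-POP pack holds 24 active and 4 placebo tablets; an n-POP pack holds 28 active tablets. No section says what happens to capsules left over on day 56.

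**Pregnancy and bleeding.** The table in section 3 lists pregnancy at 4 and 8 weeks as "Self-reported new pregnancy, pregnancy intendedness, whether planning to continue the pregnancy or not, and pregnancy outcome: continued, terminated, pregnancy loss". The week-8 questionnaire asks about "any new pregnancies and respective pregnancy outcomes if available". Bleeding over the past month is estimated at the same two times.

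**Adverse events.** Section 8.3.4 has the investigator ask about events at each study visit and follows recorded events until they resolve or stabilise. The only in-person visit described in section 8.1 is at week 4.

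**The concern.** The supply and the follow-up are both 56 days long, but they are counted from different days. Follow-up counts from delivery, and the capsules count from day 5-7. The capsules therefore outlast the contacts, and nobody is scheduled to ask a woman anything once her dosing has ended.

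Three things are at stake:

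- New maternal or infant events during the last capsules, or just after them, are not actively asked about.
- The d-POP regimen includes hormone-free days and bleeding is a listed outcome, yet the end of the second pack is not seen.
- Pregnancy is the event the pills are meant to prevent. It is asked about by self-report only, and the last query comes before the last capsule.

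The stated purpose of the pilot is to inform a larger trial, which could inherit the same schedule.

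**Working it through.** **Inputs.** Day 0 is delivery.

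- End of follow-up: 8 weeks postpartum (section 4.2; Surveys in 8.1).
- First capsule on day s, with s = 5 to 7 (120-168 hours, Randomization in 8.1).
- Supply: 2 packs of 28, one capsule a day (same place).
- d-POP pack: 24 active and 4 placebo. That the placebo tablets come last is my assumption; the text says only that tablets are packed in order of daily use.

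**The plan's own figure.** 8 × 7 = day 56. The plan states no last-capsule day.

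**Formulas.** Last capsule = s + 56 − 1 = s + 55. Capsules after day 56 = (s + 55) − 56 = s − 1. Last active d-POP tablet = s + 28 + 23 = s + 51. Second hormone-free set = days s + 52 to s + 55. First hormone-free set (Group 1 only) = days s + 24 to s + 27.

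| | s = 5 | s = 6 | s = 7 |
|---|---|---|---|
| Last capsule (day) | 60 | 61 | 62 |
| Capsules after day 56 | 4 | 5 | 6 |
| of which active, n-POP | 4 | 5 | 6 |
| Last active d-POP (day) | 56 | 57 | 58 |
| Active d-POP after day 56 | 0 | 1 | 2 |
| Second hormone-free set (days) | 57-60 | 58-61 | 59-62 |
| First hormone-free set, Group 1 (days) | 29-32 | 30-33 | 31-34 |

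In Group 3 the first pack is all placebo, so its only d-POP hormone-free days are the second set, wholly after day 56. Group 1's first set lies inside follow-up and falls within the one-month bleeding recall at week 8 (days 29-56 if a month is read as 28 days).

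**Does another reading of the text close the gap?**

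- *Start window of 120-160 hours (section 6.1).* 160 / 24 = 6.67, so the last capsule falls on day 60 to 6.67 + 55 = 61.67. The gap remains.
- *Eight weeks from enrollment (section 4.1).* Enrollment on day e ends follow-up on day e + 56, which is day 56-63 for e = 0 to 7. This reaches the last capsule only if e + 56 ≥ s + 55, that is e ≥ s − 1: day 4 or later for a day-5 start, day 6 or later for a day-7 start. Section 8.1 has staff approach women during the hospital stay. Its length is not given, but enrollment on day 2, for example, leaves (s + 55) − 58 = s − 3, or 2-4 capsules. In any case, the survey schedule still stops at the end of week 8.

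**Pregnancy.** Section 8.1 (Randomization) treats a woman as very unlikely to be pregnant before day 28 and names days 28-33 as a period of possible risk for women who no longer meet the lactational-amenorrhea criteria. Age at day 56, counted from conception: day 28 gives 56 − 28 = 28 days; day 33 gives 56 − 33 = 23 days; day 56 gives 0. The later the conception, the less likely it is to be known at week 8, and none can have reached birth. Day 28 is a counseling criterion, not a biological limit, so these ages are indicative.

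**The case against.** The best case against the point has several parts.

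- *The trial's main results do not depend on it.* Exclusive breastfeeding at 8 weeks and pill use at 8 weeks are both read at day 56. This stands.
- *Some leftover supply fits the aims.* Aim 1b measures pill use at 8 weeks, so women need pills in hand then, and the inclusion criteria ask for women who want these pills for 3 months. This explains why supply exceeds day 56. It does not explain why nobody asks about the capsules taken afterwards.
- *Later events can still be recorded.* Section 8.3.4 lets events reach staff through the participant and follows them to resolution; section 9.4.4 records them when the team learns of them. Neither sets a week-8 cut-off. This stands: what is missing is an active query, not the ability to record. A reader might infer from the seriousness criterion "or a congenital anomaly/birth defect" that such an event after an on-study conception could not be captured. The text does not support that.
- *The listed pregnancy outcomes are not all out of reach.* Continuation and the plan to continue can be answered at week 8, an early loss or termination can occur before day 56, and the questionnaire asks for outcomes only where available. A reader might conclude that the listed outcomes fall outside observation. They do not. Only the final outcome of most on-study pregnancies does.
- *The placebo month is not the cause.* It is tempting to link missed pregnancies to Group 3's placebo pack. Section 8.1 confines the assignment-related risk to days 28-33 and holds all study drugs effective after day 33. Conceptions on days 28-33 are the oldest at week 8, hence the likeliest to be known. The ones most easily missed come later and are not tied to assignment.
- *A late reply may come after the last capsule.* Section 7.3 allows surveys to be re-sent within a week. That helps only late responders, and by chance.

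**Conclusion.** The point holds in a limited form. A fully adherent woman takes 4-6 blinded capsules after her last scheduled contact, and no safety or pregnancy query follows the end of dosing. The gap in active exposure is mainly in the n-POP arm (4-6 active capsules, against 0-2 in the d-POP arms). Group 3's only hormone-free days go unobserved, while Group 1's first set is seen. The d-POP figures rest on the placebo tablets coming last; the total of 4-6 does not. All figures assume one capsule a day without interruption.

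For pregnancy the conclusion is qualitative: recent conceptions may be unknown at week 8, and most final outcomes would be. A reader might want a percentage missed. That would need a recognition lag and a distribution of conceptions over days 28-56; the documents give neither, nor an expected pregnancy rate, so no share can be computed.

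The primary outcome is unaffected. In a 30-woman feasibility pilot this is an inexpensive safety improvement worth making, not a flaw that undermines the trial.

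**What to change.** Keep week 8 as the efficacy time point. In sections 4.2 and 8.3.4 add one short closing survey link or call after the last dispensed capsule: day 62 or later, and preferably late enough for a conception around day 56 to be recognised. It should ask about maternal and infant adverse events, the date of the last capsule, bleeding, and any new pregnancy. State that a pregnancy reported then or at week 8 is followed to its outcome by telephone or record review.

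Reconcile the following so that the day on which observation ends is stated relative to the supply:

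- the anchor for 8 weeks (enrollment in 4.1, delivery in 4.2);
- the start window (160 hours in 6.1, 168 hours in 8.1);
- the week-8 contact (a visit in 4.2, an emailed survey in 8.1);
- the number of capsules dispensed against the end of participation. Which of these governs is for the sponsor to decide.

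**Cost.** One extra survey and gift card for each of 30 women, occasional follow-up of a pregnancy, and consent wording. The one drawback is a safety contact that falls outside the stated 8 weeks of participation.

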## 5 STUDY POPULATION

Postpartum women delivering a baby at University of California, San Diego (UCSD) within the past 7 days will be eligible. 30 women will be enrolled. Participants will be screened for eligibility according to the below criteria using a screening checklist. If eligible and interested in participating, a consent form will be signed.

### 5.1 INCLUSION CRITERIA

There will be a total of 30 postpartum women enrolled in this study. Participants will need to meet the following criteria:

- Are 18 years of age or older
- Desires to use POPs for 3 months
- Speak English or Spanish
- Had a vaginal or cesarean delivery of a singleton full term ( $\geq 37$  weeks) infant less than 168 hours prior
- Intends to breastfeed exclusively for 6 months

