### 5.2 EXCLUSION CRITERIA

An individual who meets any of the following criteria will be excluded from participation in this study:

- Desire another pregnancy in less than 6 months
- Do not intend to exclusively breastfeed
- Do not have access to a telephone
- Have any medical contraindication to POPs
- Have any contraindication to breastfeeding, including maternal illegal drug use, history of breast augmentation or reduction, infant with major congenital anomaly
- Cognitively impaired
- Currently incarcerated

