#### **Enrollment Procedures:**

We will assess women who indicate that they desire POPs for contraception for eligibility after they have received contraceptive counseling. Research staff will identify postpartum women who are planning on utilizing POPs as postpartum contraception via review of medical records of patients receiving inpatient obstetrical services at UCSD. Study staff will visit these potential participants during their inpatient hospital stay to present the study and administer the pre-screening eligibility form if the patient is interested in participation. While only women who intend to use POPs for at least 8 weeks will be enrolled, all participants will be told if they are unhappy with POPs at any time, the study team will facilitate timely contraceptive counseling and referral to an appropriate provider to ensure that they can switch contraceptive methods at any time if they choose.

After enrollment and prior to randomization, participants will be asked to complete a brief self-administered demographic questionnaire using a private secure tablet that enters data directly into REDCap (Research Electronic Data Capture), a secure electronic data collection system. Demographic characteristics collected will include maternal age, race, Body Mass Index, gestational weight gain, parity, education, previous experience breastfeeding, previous contraceptive use history, breastfeeding intentions, delivery type and complications, infant stay in neonatal intensive care unit (and length of stay), infant birth weight, race, sex assigned at birth, and gestational age at birth. Participants will receive a gift card via text or email link for completing the survey.

[figure not shown]

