## 9.4 STATISTICAL ANALYSES

### 9.4.1 GENERAL APPROACH

### 9.4.2 ANALYSIS OF THE PRIMARY EFFICACY ENDPOINT(S)

A survival analysis will be conducted to to assess time spent exclusively breastfeeding.

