### 9.4.5 BASELINE DESCRIPTIVE STATISTICS

Baseline characteristics such as demographic information (age, education level, race, ethnicity and employment status) will be collected. At the time of enrollment, questions will also be asked about pregnancy history, past use of contraception, use of donor milk and current perception of adequacy of

human milk supply. Means and proportions of respondents in each of the two groups will be compared to assess for success of randomization.

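### Formula use and exclusive-feeding status are not listed at baseline, so the survival analysis cannot separate supplementation begun before the first capsule from stopping after it

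*Combined protocol and SAP*

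**What the plan says.** - **Entry.** Section 5.1 requires that the woman "Intends to breastfeed exclusively for 6 months", and Section 5.2 excludes those who "Do not intend to exclusively breastfeed". Neither refers to feeding since birth. Enrolment is open until 168 hours after delivery.
- **Definition.** Section 3 defines exclusive breastfeeding as "own mother's milk via breast or bottle". Formula and donated milk both count as supplementation. There is no since-birth condition and no recall window.
- **Baseline data.** Section 8.1 (Enrollment Procedures) places a questionnaire between enrolment and randomisation. Its list includes "previous experience breastfeeding, previous contraceptive use history, breastfeeding intentions, delivery type and complications" and any neonatal intensive care stay, but not current feeding. Section 9.4.5 adds, at enrolment, "use of donor milk and current perception" of milk supply. Formula use and exclusive or non-exclusive status appear in neither list.
- **First feeding record.** Sections 3 and 8.1 (Surveys) start the feeding categories and supplement types at the end of week 2.
- **First capsule.** Section 8.1 (Randomization) gives 120-168 hours after delivery and Section 6.1 gives 120-160 hours. These windows should be reconciled.
- **Outcome and analysis.** Section 9.1 names the proportion exclusively breastfeeding at 8 weeks as primary. Section 9.4.2 plans a survival analysis "to assess time spent exclusively breastfeeding", without a time origin, an event rule or a rule for women not exclusive at time zero.

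**The concern.** Five to seven days of feeding take place before any study drug. Infants who stayed in intensive care are not excluded, and asking about donor milk suggests that the plan itself expects some early supplementation. An infant who starts formula on day 2 and is still receiving it at week 2 is first seen as non-exclusive after treatment has begun. Nothing in the listed data separates that infant from one whose mother stopped exclusive feeding on day 10.

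Such events cannot reflect pill type or timing. Section 4.1 hypothesises no clinically meaningful effect on breastfeeding, so events unrelated to treatment push the result towards the expected answer. Section 2.2 says that the pilot is to inform a large trial, so the same gap could be carried forward.

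**Working it through.** **The plan's own figure.** Section 9.2 bases N = 30 on accrual: 30/6 = 5 per month, against 180/36 = 5 per month for the larger trial. The two rates agree. The plan states no power, effect size or margin, so there is no power figure to reproduce.

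**Interval before the first feeding record.** The end of week 2 is day 14. Capsules start on days 5 to 7, so the interval is 14 − 7 = 7 to 14 − 5 = 9 days.

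**Assumed input.** Let q be the share of infants supplemented before the first capsule and still supplemented at week 2. The documents give no value. I take 10%, 20% and 30%, with 50% as an extreme. Expected numbers per arm of 10 are 10q = 1, 2, 3 and 5.

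**Expected false difference.** Randomisation gives every arm the same q in expectation, so with no pill effect the expected difference is q − q = 0.

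**Dilution.** If S(t) is the proportion still exclusive at time t among infants exclusive at the start, the observed curve from week 2 onwards is (1 − q) × S(t). A true difference D is then seen as (1 − q) × D. Assume 80% against 50%, so D = 30 points:

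| q | Observed proportions | Observed difference |
|---|---|---|
| 0% | 80% vs 50% | 30 points |
| 10% | 72% vs 45% | 0.9 × 30 = 27 points |
| 20% | 64% vs 40% | 0.8 × 30 = 24 points |
| 30% | 56% vs 35% | 0.7 × 30 = 21 points |
| 50% | 40% vs 25% | 0.5 × 30 = 15 points |

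**The 8-week proportion.** Suppose a share r of the early-supplemented infants is back to exclusive feeding at 8 weeks, equal in both arms. The arm proportions are (1 − q) × 0.8 + q × r and (1 − q) × 0.5 + q × r. The term q × r cancels, so the difference is again (1 − q) × 30 points. This holds only if the pill does not affect return to exclusive feeding. Not every early-supplemented infant is a failure here: at q = 20% and r = 50% the proportions are 74% and 50%, not 64% and 40%.

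**Chance imbalance.** Let X and Y be independent Binomial(10, q) counts of early-supplemented infants in two arms. Summing b(i; 10, q) × b(j; 10, q) over all pairs with |i − j| at or above the gap gives:

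| q | Gap of 2 or more | Gap of 3 or more |
|---|---|---|
| 10% | 24% | 6% |
| 20% | 39% | 16% |
| 30% | 46% | 22% |

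**The case against.** The strongest reply is that this is a 30-woman pilot sized on accrual. Even with q = 0, the exact Fisher power to detect 80% against 50% with 10 per arm is about 13%, so dilution changes no decision in the plan. The imbalance figures are also ordinary sampling variation: any outcome with a rate of 40% to 50% gives a gap of 2 or more in 49% to 50% of trials. The largest departure from equality that a gap of 2 can show is 0 against 2 of 10, where the two-sided Fisher p is 2 × 45/190 = 0.47. Entry by intention may be a deliberate, pragmatic choice. All of this stands, and it makes the point a cheap improvement, not a threat to the pilot. It does not supply the missing baseline status.

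A reader might infer three stronger claims that the documents do not support.

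- **That nothing about feeding is recorded before treatment.** Section 9.4.5 lists donor milk and perceived supply. The questionnaires themselves are not in the documents, so the gap is in the listed items.
- **That early-supplemented infants are failures of the primary outcome.** Section 9.1 reads status at 8 weeks and Section 3 sets no since-birth condition. An infant given formula on day 2 and only its mother's milk at week 8 is a success. A short supplement that has ended by week 2 need not appear in the surveys either.
- **That these events would be falsely attributed to a pill.** The contrasts are randomised and blinded, so the expected false difference is zero.

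**Conclusion.** The point holds as a gap in the baseline data and in the definition of the survival analysis. With the listed items, supplementation begun before the first capsule and persisting to week 2 cannot be told from stopping after it. The result is dilution by the factor 1 − q, plus chance imbalance that could be neither seen nor adjusted for where the supplement was formula. The sizes rest on assumed values of q and, for the difference in points, on an assumed 80% against 50%. The 8-week proportion is affected only where early supplementation persists, or if exclusivity were read as since birth, which no section states. This is more than an unwritten detail of the analysis, because the status is not among the planned data and could later be recovered only by recall.

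**What to change.** 1. Add to the pre-randomisation questionnaire the infant's current feeding category, using the Section 3 categories, and any formula, donor milk or other feed since birth, with dates.
2. In the week-2 survey, ask for the date of any first supplement. This covers the days between the questionnaire and the first capsule.
3. In Section 9.4.2, state whether the clock starts at randomisation or at the first capsule. If it is the first capsule, record its actual date, since Section 3 lists timing only as assigned. Define the event. Include in the risk set only infants exclusively fed at the origin, and report the others by arm.
4. Drop no randomised woman from the 8-week proportion because of baseline feeding. State that it is current status at 8 weeks, with a stated recall window, and show it by baseline feeding status.
5. Reconcile the baseline lists in Sections 8.1 and 9.4.5.

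The cost is one or two baseline items, one week-2 item and some protocol wording. Eligibility, visits and treatment do not change. The survival risk set becomes slightly smaller, but women leave it only for feeding status that precedes the chosen origin. The items should be in place before enrolment, because later collection would rely on recall.
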